13.2 Secondary endpoints

The following secondary efficacy endpoints will be analyzed in the study:

- 1) Total dehiscence rate of target incision/laceration assessed at the Month 1 visit.
- 2) Subject completed POSAS done at the Month 1 and Month 3 visits.
- 3) Wound infection incidence between both treatment groups, with two analyses:
 - 3.1) Wound infection incidence assessed at the Day 10, Month 1, and Month 3 visits.
 - 3.2) Wound infection assessed on a binary scale
- 4) Evaluation of the medical practitioner satisfaction with the Device, with two analyses:
 - 4.1) Investigator completed POSAS done at the Month 1 and Month 3 visits.
 - 4.2) Investigator completed mHCS at Day 10 and Month 1 visits.
- 5) Evaluation of the subject comfort with the Device during and after treatment.
- 6) Evaluation of the medical practitioner overall satisfaction and ease of use with the Device during and after the closure of the target surgical incision/laceration.

All analyses for secondary endpoints will be performed on the FAS.

13.2.1 Total dehiscence rate at Month 1

The total dehiscence rate of target incision/laceration assessed at the Month 1 visit will be analyzed descriptively only by using the same descriptive statistics described in Section 13.1.1. For this analysis, all evaluations of dehiscence until Month 1 (at Day 1, Day 10, Month 1 or other unscheduled visits before Month 1) will be included in the analysis. Thus, if the wound is assessed as showing dehiscence at Day 1 or Day 10 but showing no dehiscence at subsequent visit(s), dehiscence will be evaluated as “Yes”.

13.2.2 Subject completed POSAS

The Patient and Observer Scar Assessment Scale (POSAS) is a questionnaire developed to assess scar quality which contains 6-item scales (observer and patient scale), both of which are scored on a 10-point rating scale. Moreover, each scale has an overall “opinion” to compare the pain and itching of the scar compared to normal skin (with a value of 1 indicating no pain and no itching, and a value of 10 indicating worst scar imaginable with pain and itching).

The subject completed POSAS will be recorded in the e-CRF at Month 1, Month 3 and the Early Discontinuation (ED) visit. For the analysis of this endpoint, descriptive statistics of each of the 6-item scales plus the overall “opinion” will be presented by visit.

13.2.3 Wound infection

Wound infection evaluation, diagnosed according to the CDC criteria for surgical site infection, will be assessed by a treating physician and recorded in the e-CRF.

13.2.3.1 Wound infection incidence at Day 10, Month 1 and Month 3

Wound infection incidence, evaluated through the presence of erythema, edema, pain at rest or elevated temperature, will be summarized with descriptive statistics at the Day 10, Month 1, and Month 3 study visits.

13.2.3.2 Wound infection evaluated with a binary scale

Wound infection will be additionally assessed at the same timepoints by calculating a Wound Infection Score utilizing a binary scale as follows:

$$\text{Wound Infection Score} = I_{\text{erythema}} + I_{\text{edema}} + I_{\text{pain_rest}} + I_{\text{elevated_temperature}},$$

where the four indicator variables above are equal to 1 if the wound reported the presence of erythema, edema, pain at rest or elevated temperature, and equal to 0 if the presence of each category is not recorded or is missing. Thus, the Wound Infection Score will have a maximum value of 4, and a minimum value of 0.

Descriptive statistics of the Wound Infection Score will be presented by visit.

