## 8.2 Follow-up Period

Subjects treated for lacerations may not be able to attend the Day 1 visit since they are usually not hospitalized. In this case, all attempts should be made to obtain information on potential dehiscence and AEs by phone. The reason for non-attendance should also be reported.

In case a subject is not able to attend the Day 10 visit, a telephone call can be done to capture the primary endpoint variables information. However, this is only allowed for exceptional cases and the reason for non-attendance and potential dehiscence and AEs should be recorded.

### 8.2.1 Day 1

The following procedures will be performed at Day 1:

- Record concomitant medication.
- Record AEs.
- Record of incidents and device performance, device-related complaints.
- Evaluation of dehiscence (incidence and grading).

### 8.2.2 Day 10 and Month 1

The product-related questionnaire will be completed by the investigator only once per site when the last subject randomized at the site completes the Month 1 visit.

The following procedures will be performed at both Day 10 and Month 1:

- Record concomitant medication
- Record AEs
- Record of incidents and device performance, device-related complaints

- 
- Evaluation of dehiscence (incidence and grading)
  - Evaluation of wound infection, if an infection occurred (incidence and criteria score)
  - Modified Hollander Cosmesis Scale (mHCS) completed by investigator
  - Subject-completed satisfaction questionnaire

Additional procedures performed at Month 1 include:

- Patient and Observer Scar Assessment Scale (POSAS), completed by subject and investigator
- Subject-related questionnaire completed by investigator
- Collect subject diary

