16.1.1.7 Handling of missing values

At each time point/visit, all subjects still in the trial (i.e., subjects who have not been withdrawn from the study) are reported. Missing values will be taken into account as missing in the analysis, unless specified differently (e.g., primary efficacy analysis). The number of observed values and the number of missing values must add up to the number of subjects in the trial at the respective time point/visit.

Unless otherwise specified in the SAP, missing values will not be imputed (with the sole exception of primary efficacy data, as discussed in Section 13.1.1). If missing values are imputed, the result of all imputation strategies and newly derived information must be stored in the ADaM data set.

Imputed values will be listed in the subject data listing and marked as imputed.

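### The Wound Infection Score gives 0 to subjects whose wound was not assessed at a visit, so an unassessed wound counts as a clean one

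*SAP*

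**What the plan says.** SAP Section 13.2.3.2 defines the Wound Infection Score as the sum of four 0/1 indicators: erythema, edema, pain at rest and elevated temperature. An indicator is 1 if the sign was reported, and "equal to 0 if the presence of each category is not recorded or is missing". The section adds: "Thus, the Wound Infection Score will have a maximum value of 4, and a minimum value of 0". On the analysis it says: "Descriptive statistics of the Wound Infection Score will be presented by visit". SAP Section 14.3 repeats the wound infection analysis on the safety set.

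SAP Section 16.1.1.7 gives the general rule: "Unless otherwise specified in the SAP, missing values will not be imputed (with the sole exception of primary efficacy data". It also says: "Missing values will be taken into account as missing in the analysis, unless specified differently (e.g., primary efficacy analysis". At each visit, "all subjects still in the trial (i.e., subjects who have not been withdrawn from the study) are reported", and observed plus missing counts must add up to that number. Table 2 in SAP Section 16.1.1.2 includes a count of missing values among the descriptive statistics.

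On data collection, Protocol Section 8.2 lists for Day 10 and Month 1: "Evaluation of wound infection, if an infection occurred (incidence and criteria score". Month 3 and Early Discontinuation carry the same condition. Section 8.2 also allows a telephone call in exceptional cases when a subject cannot attend Day 10. The call is meant to obtain the primary endpoint information, with potential dehiscence and adverse events recorded.

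**The concern.** Under the stated rule a score of 0 can come from three situations that the output cannot tell apart:

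- the visit took place and no infection was recorded;
- the wound was infected but no sign was recorded;
- the wound was not assessed at that visit.

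The plan itself creates the third case. A subject who misses a visit without withdrawing stays among those reported. A Day 10 telephone contact supplies dehiscence and adverse event information but no examination of the wound, so redness, swelling and local warmth cannot be observed.

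The score is a secondary endpoint and is repeated as a safety summary. Coding unknown as absent is the favourable assumption for a safety measure, and no sensitivity analysis accompanies it. By contrast, the primary endpoint has an analysis that counts missing as failure (SAP Section 13.1.2), and missing adverse event dates are imputed conservatively (SAP Section 16.1.4.1). The trial is open-label, so equal completeness of recording in the two arms cannot be taken for granted.

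**Working it through.** **Inputs.** The coding rule and score range are from SAP Section 13.2.3.2. The reporting rule is from SAP Section 16.1.1.7. The total of 189 subjects is from Protocol Section 10.2. The 3.6% infection rate is from Protocol Section 5, which gives it for other skin adhesives; it is used below only for scale. The documents give no rate of missed assessments, so m = 5% to 20% is an assumption.

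**Step 1: the plan's own figure.** The 16 combinations of four 0/1 indicators give sums from 0 to 4, as the SAP states. Every indicator is always 0 or 1, so the sum always exists. The count of missing values required by Table 2 and Section 16.1.1.7 is therefore always zero for this score, however many wounds went unassessed.

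**Step 2: which blanks are wrongly coded.**

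| Situation at the visit | Score under the SAP rule | Correct? |
|---|---|---|
| Attended, no infection recorded | 0 | Yes, signs not collected by design |
| Still in the trial, visit missed | 0 | No, unknown |
| Day 10 by telephone, wound not examined | 0 | No, unknown |
| Infected, some signs blank | Sum of recorded signs | A lower bound |
| Already withdrawn | Not reported at that visit | No effect |

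**Step 3: effect on the mean.** Let N subjects be reported, a fraction m unassessed, and mu the mean among those assessed. Then

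coded mean = [(1 - m) x N x mu + m x N x 0] / N = (1 - m) x mu.

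Reading mu as the true mean requires missingness to be independent of true status.

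| True mean | m = 5% | m = 10% | m = 20% |
|---|---|---|---|
| 1.0 | 0.95 | 0.90 | 0.80 |
| 0.5 | 0.475 | 0.45 | 0.40 |

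**Step 4: effect on the arm difference (MAR-CUTIS minus Dermabond).** With equal true means mu, the difference is mu x [(1 - m_M) - (1 - m_D)] = mu x (m_D - m_M). For mu = 1.0:

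- 10% missing in both arms: 0;
- 15% versus 5%: -0.10;
- 5% versus 15%: +0.10.

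If the true means differ and m is the same in both arms, the difference shrinks by the factor (1 - m). For scale, with 3.6% infected and an assumed 3 signs each, the mean is 0.036 x 3 = 0.108, and 15% versus 5% missing gives 0.108 x (0.05 - 0.15) = -0.011.

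**Step 5: what the repair must avoid.** Two simple alternatives do worse than the SAP rule.

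- *Treat every blank as missing.* The signs are collected only for infected wounds, so the mean over available records in the last example would be 3.0 instead of 0.108.
- *Drop an infected wound if any sign is blank.* Take 0.036 x 189 = 6.8, about 7 infected, each assumed to score 4 truly. The true mean is 28/189 = 0.148. With one sign unrecorded in one subject, the SAP rule gives 27/189 = 0.143 (-3.6%). Dropping that subject gives 24/188 = 0.128 (-13.8%).

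**The case against.** The strongest defence is that the rule largely fits the data collection. The signs are recorded only if an infection occurred, so for most attending subjects a blank means no infection, and 0 is the right value. This stands. It limits the problem to unassessed wounds and incomplete records.

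A reader might infer that the rule breaches the SAP's own ban on imputation. The documents do not support that. The general rule yields wherever the SAP specifies otherwise, Section 13.2.3.2 is such a specification, and Protocol Section 10.1.5 leaves missing-data rules for other variables to the SAP. What remains is loose wording: primary efficacy data are called the only exception, yet Section 13.2.3.2 and the adverse event date imputation in Section 16.1.4.1 are exceptions too.

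A reader might also infer that every missed visit adds a zero. Withdrawn subjects are not reported at later visits, so they add none there.

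Nor is missingness wholly hidden. Infection incidence is summarised separately at the same visits, and SAP Section 8.1 displays a missing category for categorical variables when missing values occur. The score itself still shows none.

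Finally, all non-primary endpoints are descriptive, no safety comparison is tested, and both arms follow the same rule. That limits the consequence, but does not make 0 the right value for a wound nobody assessed.

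**Conclusion.** The concern holds for wounds not assessed at a visit in subjects still in the trial. They are scored as clean, and the score's missing count is zero by construction. The bias in the score can only be downward. Its size is 5% to 20% of the mean for an assumed 5% to 20% unassessed, if missingness is independent of true status; the actual rate is not in the documents. With equal true means, a spurious arm difference arises only if missingness differs by arm, and nothing in the documents shows that it will.

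It is tempting to reason that one of about 7 infected subjects coded 0 would cut the total score by 1/7, or 14%. That needs all four signs blank for that subject and similar scores among the infected, and it treats a background rate for other adhesives as this trial's rate. It should not be quoted as the expected size.

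Alpha, power, sample size and the primary conclusion are unaffected. This is a correction to a descriptive secondary and safety summary.

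**What to change.** In SAP Section 13.2.3.2:

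- Set the score to 0 only when the infection assessment was done and no infection was recorded.
- Set it to missing when the assessment was not done, including a missed visit or a Day 10 telephone contact without wound assessment. Show the number missing by visit and arm.
- For an infected wound with some signs missing, keep the subject and the recorded signs. Show each sign with its own missing count, and report the score as a minimum or with a range.

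In SAP Section 16.1.1.7, replace the wording "missing values will not be imputed (with the sole exception of primary efficacy data" with text that agrees with Section 13.2.3.2 and with the adverse event date imputation in Section 16.1.4.1.

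The cost is a few sentences, slightly more derivation and display work, and a smaller denominator for the score at visits with unassessed wounds.

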13.2.4 Evaluation of the medical practitioner satisfaction with the Device

The satisfaction of the medical practitioner with the cosmetic outcome after the closure of the target surgical incision/laceration will be evaluated with the two questionnaires described below.

13.2.4.1 Investigator completed POSAS

The investigator completed POSAS will be recorded in the e-CRF at Month 1 and Month 3. Similarly as for the subject completed POSAS described in Section 13.2.2, this questionnaire contains a 6-item scale and an overall “opinion” to compare the pain and itching of the scar after the closure of the surgical incision/laceration. Additionally, the investigator completed POSAS also contains a categorization of each parameter to describe further the state of the scar.

For the analysis of this endpoint, descriptive statistics of each of the 6-item scales, the categorization of each parameter and the overall “opinion” will be presented by visit.

13.2.4.2 Investigator completed mHCS

The investigator completed Modified Cosmesis Scale (mHCS) contains 6 wound characteristics measurements to describe the scar after wound closure. Each characteristic is graded on a 0 (no/good) or 1 (yes/poor) point scale. A total cosmetic score is derived by the addition of the six characteristic-scores. The mHCS will be analyzed as recorded in the e-CRF at Day 10 and Month 1.

For the analysis of this endpoint, descriptive statistics of each of the six characteristic-scores and the total cosmetic score will be presented by visit.

13.2.5 Subject comfort with the Device

A subject-completed questionnaire to evaluate the comfort with the Device during and after treatment will be done at the Day 10 and Month 1 visits, and recorded in the e-CRF.

The questionnaire for Day 10 contains two main blocks of questions:

- The first block examines the wound pain experienced at the area of the wound, and should be completed with a value between 0 and 100 to rate the wound pain.
- The second block consists of 5 yes/no questions that evaluate the subject's experience and ease of use with the Device.

The questionnaire for Month 1 also contains two main blocks of questions:

- Similarly as for the questionnaire at Day 10, the first block examines the wound pain experienced.
- The second block consists of 2 yes/no questions that evaluate the subject's satisfaction and preference with the use of the Device.

Descriptive statistics for each question of both questionnaires will be presented for the analysis of this endpoint.

The complaints with the the device recorded in the Subject e-diary will be listed.

13.2.6 Medical practitioner overall satisfaction and ease of use with the Device

For the evaluation of the overall satisfaction of the medical practitioner with the Device during and after the closure of the target surgical incision/laceration two questionnaires will be applied:

- 1) Product-related questionnaire for Investigators, to be completed for each center when the last randomized subject at the center completes the D10 visit. The same questionnaire will be completed for both MAR-CUTIS and Dermabond.

This questionnaire consists of 8 yes/no questions and 1 opinion question that evaluate the investigator's experience with use of the adhesive (i.e., instructions easy to understand, preparation of the syringe being easy and fast, glue hardening time).

- 2) Subject-related questionnaire for Investigators, to be completed at the Day 0 and Month 1 visits, and recorded in the e-CRF.
 - The questionnaire for Day 0 consists of 5 yes/no questions that assess the investigator's experience applying the adhesive (i.e., easy to use, fast, without complications, time saving and reduced efforts).
 - The questionnaire for Month 1 consists of a visual analog scale that rates usability of the product from 1 to 100, and two questions that evaluate the experience with the adhesive and the pain or burning at the time of application. Moreover, it also contains additional questions to describe the event of a premature removal of the adhesive.

Descriptive statistics for each question of both questionnaires will be presented for the analysis of this endpoint.

13.3 Additional exploratory analysis

For secondary endpoints only, the following additional analysis will apply: if the assessment is performed at the ED visit, descriptive statistics for the ED visit and the combined ED plus last planned assessment (at visit Month 1 or Month 3) will also be presented.

14 SAFETY ANALYSES

No statistical tests for comparison of safety data between treatment groups will be performed.

Safety data will be summarized descriptively by treatment group and overall.

All safety data will be presented for the SAF unless otherwise specified.

14.1 Adverse events

A treatment emergent adverse event (TEAE) is defined as any adverse event that, based on start date information, occurs in the on-treatment-period as defined in Section 8.2.2. This includes any events related to the procedures, the IMD, or the comparator.

A pre-treatment non-TEAE is an adverse event starting in the pre-treatment period as defined in Section 8.2.2.

A serious adverse event (SAE) is any untoward medical occurrence of effect that:

- Led to death, or
- Led to serious deterioration in the health of the subject, or
- Led to fetal distress, fetal death, or a congenital abnormality or birth defect.

This includes device deficiencies that might have led to a SAE. More details on the definition of SAEs are available in Protocol Section 9.3.1.

If there are partial dates or times, an adverse event will be considered treatment emergent unless the information available will clearly exclude it. Further details can be found in Section 16.1.4.1.

Assignment of TEAEs to treatment will be based on the definition of the on-treatment-period given in Section 8.2.2, thus, TEAEs occurring during the on-treatment period are assigned to the respective treatment.

The causal relationship of TEAEs to IMD is categorized as follows:

Category	Assessment by investigator
Related	probable certain/very likely possible
Not related	unlikely unrelated

An Adverse Device Effect (ADE) is an AE related to the use of an IMD. This includes any AE resulting from insufficiencies or inadequacies in the instructions for use, deployment, implantation, installation, operation or any malfunction of the IMD. ADEs are a subset of TEAEs.

An ADE that results in any of the consequences characteristic of a SAE will be considered as a serious ADE.

Serious ADEs which by its nature, incidence, severity or outcome have not been identified in the current version of the MAR-CUTIS risk analysis report or Instructions for use for Dermabond Advance (see Protocol Section 15.2 for more details) will be considered as unanticipated ADEs. Anticipated ADAs are defined as events that have been previously identified in applicable product information.

The following overview tables will be generated by treatment group and overall.

1. Summary of the number and percentage of subjects with at least 1 of the following events, and of summary of the number and percentage of TEAEs for:
 - TEAEs.
 - Serious TEAEs.
 - Non-serious TEAEs.
 - TEAEs leading to withdrawal from the trial.
 - ADEs.
 - Serious ADEs.
 - ADEs leading to withdrawal from the trial.
 - Anticipated/Unanticipated ADEs
 - TEAEs/ADEs with fatal outcome.

The percentage denominator will be the number of subjects by treatment group in the SAF, or the number of TEAEs, respectively.

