### Study Duration:

The overall study duration for each subject is up to 4 months:

- Day -21 to Day 0: screening, presurgical examination.
- Day 0: presurgical examination, surgery, final eligibility, allocation to treatment group, treatment.
- Follow-up visits: Day 1, Day 10, Month 1, and Month 3 or Early Discontinuation.

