## 9.3.2 Safety Reporting

### 9.3.2.1 Documentation and Reporting of Adverse Events

Adverse events should be reported and documented in accordance with the procedures outlined below. All AEs occurring during the study must be documented on the relevant eCRF pages. The following data should be documented for each AE:

- Description of the symptom event
- Classification of ‘serious’ or ‘not serious’
- Severity
- Date of first occurrence and date of resolution (if applicable)
- Action taken
- Causal relationship
- Outcome of event (unknown, recovered, not yet recovered, recovered with sequelae, death [with date and cause reported])

The investigator will record all AEs from the time following the signature of informed consent/assent until the last visit of the subject or later in case of ongoing AEs.

It is the responsibility of the investigator to document all AEs that occur during the study. Adverse events may be directly observed, evident in laboratory or diagnostic results, reported spontaneously by the subject, or by questioning the subject at each study visit. Subjects should be questioned in a general way, without directly prompting about the occurrence of any specific symptoms (eg, “How have you been feeling since the last visit?”). Adverse events should be reported on the appropriate page of the eCRF.

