8.2.2 Further definitions

Baseline	Baseline is defined as the last observation (scheduled or unscheduled) before application of the IMD (i.e., D0), if not otherwise specified.
----------	--

Investigational Medical Devices (IMD)	- MAR-CUTIS: a polyurethane-based skin adhesive, used for topical closure of incisions and surgical wounds replacing the last dermal suture line. - Dermabond Advanced: a topical skin adhesive used to hold closed easily approximated skin edges of wounds from surgical incisions, and simple, thoroughly cleansed, trauma-induced lacerations.
On-treatment-period	After the start of the application of the IMD (D0) until the end-of-treatment visit (Month 3).
Pre-treatment-period	Before the start of the application of the IMD, i.e. D-21 to D0.
Trial completers	Trial completers will complete the screening-presurgical examination visit (Day -21 to D0), the D0 visit, and at least the Month 3 follow-up visit.

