12 EXPOSURE AND COMPLIANCE

12.1 Exposure

Exposure to the IMD will be presented in days and summarized for each subject using the following formula:

Treatment exposure = date and time of glue detachment or removal – date and time of application of the IMD

For the formula above, the time of glue detachment or removal will be used only if it is recorded in the e-CRF (recorded for on-site assessments, but not recorded for the subject diary).

If no glue detachment or removal was applicable, the exposure will be calculated instead with the formula:

Treatment exposure = date of study completion or early withdrawal – date and time of application of the IMD

Treatment exposure will be reported in days rounding to one decimal place.

Treatment exposure will also be assessed using the following (as recorded in the e-CRF for IMD application and performance):

- Number of syringe(s) used for glue application
- Total volume used (mL)

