16.1.4 Safety analysis

16.1.4.1 Adverse events

[figure not shown]
The result of all imputation strategies (e.g., incomplete start dates of adverse events and new derived information (e.g., treatment-emergent flag) must be stored in ADaM data set.

Handling of missing date information

The term missing date refers to a completely missing date or to an incomplete date where parts are not available.

The following imputation strategy is applied.

Missing start and end date will be imputed conservatively, i.e., missing values will be imputed in such a way that the duration of the adverse event is considered with the longest possible duration and such that, whenever the adverse event may potentially start after first IMD application, the adverse event will be handled as a TEAE.

I1-I4: imputation steps

C1-C4: checkpoints

AE = adverse event, IMP = investigational medicinal product

Figure 2: Graphical overview about the imputation strategy

Further explanations on the flow chart:

The different steps of the displayed imputation strategy must be completed from the first to the last step. All procedures in each step must be completed in the order given.

- Imputation:
 - I1: Impute with date of the start of the application of IMD
 - I2:
 - a) Impute with first calendar day and/or first calendar month
 Imputation will be done based on the available partial information starting with month and then day. The respective first month and day will be chosen for imputation:

Missing date	Imputed date
2014-Mar	2014-Mar-01
2014	2014-Jan-01

- I3: Impute with date of informed consent signed
- I4:
 - a) Impute with last calendar day and/or calendar last month
 Imputation will be done based on the available partial information starting with month and then day. The respective last month and day will be chosen for imputation:

Missing date	Imputed data
2014-Mar	2014-Mar-31
2014	2014-Dec-31

For February leap years must to be taken into account when calculating the last day in February.

1.1.

- Checkpoints
 - C1: The decision must be taken based on the available information (date) before imputation.
 - C2: Adverse event stop date before the start of the application of IMD

1.2. 1) The decision must be taken based on the available information (date) before imputation.

2) If the end date is completely missing (with or without the information that the adverse event was continuing), this will be considered as after the start of the application of IMD.

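### The SAP splits Day 0 at the moment of adhesive application, but the required AE onset date cannot place a Day 0 event on either side, so surgical AEs before application default to treatment-emergent

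*SAP*

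**What the plan says.** **Periods.** SAP 8.2.2 defines the on-treatment period as "After the start of the application of the IMD (D0) until the end-of-treatment visit (Month 3" and the pre-treatment period as "Before the start of the application of the IMD, i.e. D-21 to D0". The boundary is a clock moment on Day 0.

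**Classification.** SAP 14.1: "A treatment emergent adverse event (TEAE) is defined as any adverse event that, based on start date information, occurs in the on-treatment-period", with the period taken from SAP 8.2.2. For incomplete timing: "If there are partial dates or times, an adverse event will be considered treatment emergent unless the information available will clearly exclude it". SAP 16.1.4.1, under its rules for missing date information, applies the same principle: "whenever the adverse event may potentially start after first IMD application, the adverse event will be handled as a TEAE".

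**Data required.** Among the items to be documented for each AE, protocol 9.3.2.1 lists "Date of first occurrence and date of resolution (if applicable". It names no clock time. AEs are recorded from consent onwards. For the adhesive itself, the SAP 12.1 exposure formula uses the "date and time of application of the IMD".

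**Order of events.** The protocol synopsis gives "Day 0: presurgical examination, surgery, final eligibility, allocation to treatment group, treatment". Protocol 7.4.4 and SAP 5.3 place closure of the deep layers before randomisation, and the adhesive after it.

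**Use.** The main safety endpoint is AEs in the month after treatment, by severity and relatedness. SAP section 14 is descriptive, without tests. Pre-treatment events have their own tables in SAP 14.1.1.

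**The concern.** For a surgical subject, anaesthesia, the operation and deep closure all take place on Day 0 before the adhesive is opened. An AE in that interval cannot be an effect of either adhesive and, by SAP 8.2.2, belongs to the pre-treatment period. The date that the protocol requires cannot show this, and the stated default sends the event to the TEAE tables.

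Most subjects follow this course. The sample-size section assumes 85% incisions. With about 40 lacerations among 189 subjects (protocol 7.2.1), the share is (189 − 40)/189 = 79%.

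At stake is how the safety tables read. The main safety objective compares AE incidence between the adhesives. Treating doubtful events as emergent is cautious for a single-arm description. In a comparison, events common to both arms make the arms look more alike, which is not cautious for a new device. The same events would also be missing from the pre-treatment tables.

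**Working it through.** **1. Can the required data place a Day 0 AE?**

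| Element | Resolution | Source |
|---|---|---|
| Boundary between periods | moment of application on Day 0 | SAP 8.2.2 |
| Application | date and time | SAP 12.1 |
| AE onset, as required | date | Protocol 9.3.2.1 |
| Imputation steps shown in the text | date | SAP 16.1.4.1 |

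An AE dated before Day 0 is pre-treatment, and one dated after Day 0 is on-treatment. An AE dated Day 0 satisfies either definition. A Day 0 date with no time does not clearly exclude onset after application, so the SAP 14.1 default makes it a TEAE. If such a date is instead regarded as complete, so that the default for partial timing does not apply, the SAP gives no rule for ordering it and the choice falls to the programmer.

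**2. Which outputs are affected?** TEAEs, serious and non-serious TEAEs, the intensity, outcome and action-taken tables, and time to onset gain events. Time to onset is counted from application (SAP 16.1.4.1), so these events enter as same-day onsets. The pre-treatment tables lose the same events.

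ADE counts should not change, because the protocol 9.3.3.2 category for unrelated events covers an incompatible time relationship. The ADE share of events in the overview can still move, since its denominator is the number of TEAEs. With assumed counts, 20 ADEs among 60 TEAEs is 33%; with 20 surgical events added it is 20/80 = 25%.

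**3. How large could the attenuation be?** The plan gives no AE incidence and no Day 0 AE rate, so there is no planned figure to reproduce. The following inputs are assumptions.

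Let *a* be the true post-application incidence in an arm. Let *s* be the share of subjects with at least one pre-application Day 0 AE, equal in both arms and independent of later AEs.

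- Reported incidence = 1 − (1 − s)(1 − a)
- Reported difference = (1 − s)(a₁ − a₂)

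With a₁ = 20% and a₂ = 10%:

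| s | Higher arm | Lower arm | Difference (points) | Ratio |
|---|---|---|---|---|
| 0% | 20.0% | 10.0% | 10.0 | 2.00 |
| 5% | 1 − 0.95×0.80 = 24.0% | 1 − 0.95×0.90 = 14.5% | 9.5 | 1.66 |
| 15% | 1 − 0.85×0.80 = 32.0% | 1 − 0.85×0.90 = 23.5% | 8.5 | 1.36 |
| 30% | 1 − 0.70×0.80 = 44.0% | 1 − 0.70×0.90 = 37.0% | 7.0 | 1.19 |

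From 30% versus 20% (ratio 1.50), the ratio becomes 1.40 at s = 5% and 1.22 at s = 20%. The difference shrinks by the factor 1 − s, and the ratio moves further towards 1.

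**4. Chance imbalance.** Balance holds only on average. With 126 and 63 subjects, the between-arm difference in the share with a pre-application event has SD √[s(1 − s)(1/126 + 1/63)]. This is 3.4 points at s = 5%, 5.5 at 15% and 7.1 at 30%.

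**The case against.** The strongest reply is that the SAP already has the right definition. The on-treatment period begins at application, so an intra-operative AE known to precede it is pre-treatment and has a table of its own. The default yields when information clearly excludes the event, and that clause mentions times as well as dates. The 16.1.4.1 wording is about missing dates, which a complete Day 0 date is not, and its flow chart is not visible. The eCRF is not visible either and may hold an onset time. SAP 12.3 also summarises whether an AE occurred during application or since the last visit.

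Most of this stands as a limit on the claim. A reader might infer that every Day 0 AE becomes a TEAE on its date alone. The documents do not support that, because the period is anchored to application and the exclusion clause exists. Nor do they show that onset time is absent from the eCRF; they show only that the protocol does not require it. The SAP 12.3 item does not single out events before application, and no rule says how an event described as intra-operative is to be excluded.

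A reader might also infer that the main safety comparison is compromised. That goes too far. The endpoint is classified by relatedness, and pre-application events should be rated unrelated. The tables by preferred term keep surgical terms apart from wound and skin terms. Events before randomisation favour neither arm on average, and no test depends on them. What remains is that the stated default, applied to the data the protocol requires, does not deliver the SAP's own definition.

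**Conclusion.** The point holds as a gap between the definition and the data. The definition needs the order of onset and application on Day 0, the protocol requires only a date, and the default then counts the event as treatment-emergent. The consequence is a shared background in the all-cause TEAE, serious TEAE, intensity and time-to-onset summaries, a weaker descriptive contrast, and under-reported pre-treatment events. It is attenuation, not bias towards one adhesive, and ADE counts should stand.

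The conclusion rests on three assumptions: the eCRF does not capture onset time, a Day 0 date without a time is handled under the SAP 14.1 default, and randomisation follows surgery as protocol 7.4.4 and SAP 5.3 state. The size cannot be determined from the documents. The figures in the working are illustrations under assumed rates, and the fall in the ratio should not be read without the smaller fall in the difference. This is a cheap improvement worth making; the primary analysis is untouched.

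**What to change.** - **Data.** For AEs starting on Day 0, record onset as before, after or unknown relative to the start of adhesive application. If AE onset time is already collected, use it against the application time and add no item. Staff know the allocation, so the entry should be taken from the operative record where possible.
- **SAP 14.1 and 16.1.4.1.** State that a Day 0 AE is a TEAE only if its onset was after the start of application or is unknown, and that an AE with onset before application is reported as a pre-treatment non-TEAE. The cautious default then remains where the order is truly unknown.

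**Cost.** One eCRF item, two SAP sentences, and a query for Day 0 AEs already recorded. No visit or assessment is added.
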